1.0 Objectives

1.1 Describe the purpose, specific aims, or objectives of this research.

Response: To compare the efficacy of root coverage achieved by the Pinhole Surgical Technique (PST) technique and the Connective Tissue Graft (CTG) technique in the treatment of Miller class I and II gingival recession defects.

1.2 State the hypotheses to be tested, if applicable.

NOTE: A hypothesis is a specific, testable prediction about what you expect to happen in your study that corresponds with your above listed objectives.

Response: Pinhole Surgical Technique outcomes are not inferior to those of the Connective Tissue Graft surgical technique.

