4.0 Study Design

4.1 Describe and explain the study design (e.g. case-control, cross-sectional, ethnographic, experimental, interventional, longitudinal, observational).

Response: Randomized, split-mouth, double blinded design clinical trial.

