17.0 Data Management and Analysis

17.1 *Describe the data analysis plan, including any statistical procedures. This section applies to both quantitative and qualitative analysis.*

Response: The main aim of this study is to assess the efficacy of the pinhole surgical technique in treating gingival recession compared to an established surgical treatment method. We therefore will focus in this clinical trial on one primary endpoint, namely recession depth. The change in recession depth during the study observation period will therefore be used for the calculation of sample size.

We previously have calculated the sample size based on parameter estimates gathered from published studies. We now have recalculated the sample size and used parameters estimates generated from 28 cases already treated in this clinical trial. This should give more accurate parameters to calculate the sample size needed. We also used the 80% power. Accordingly, we used the following assumptions to calculate the sample size:

Standard deviation in the group A: 0.91

Standard deviation in the group B: 0.95

Correlation: 0.46

Effect size (the difference in the reduction in recession depth between the test and control groups): 0.4 mm

Level of significance: 0.05

Power: 80%

Type of test: 2-sided

Based on these assumptions, the sample size is 48. In addition, we anticipate a drop out of 4 subjects. Hence, the total number of participants needed for this study is 52.

17.2 *If applicable, provide a power analysis.*

NOTE: This may not apply to certain types of studies, including chart/records reviews, survey studies, or observational studies. This question is asked to elicit whether the investigator has an adequate sample size to achieve the study objectives and justify a conclusion.

Response: Please see item 17.1

17.3 *Describe any procedures that will be used for quality control of collected data.*

Response:

Standardization of measurement and radiographs and assurance of intraoperator reproducibility will be performed.

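### The hypothesis is non-inferiority, but the sample size is for a 2-sided test of a 0.4 mm difference and no margin is given, so the stated 80% power does not belong to the stated hypothesis

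*Protocol*

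**What the plan says.** Protocol section 1.2 states the hypothesis as non-inferiority of the pinhole technique (PST) to the connective tissue graft (CTG): "Pinhole Surgical Technique outcomes are not inferior to those of the Connective Tissue Graft surgical technique".

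Section 4.1 describes the design as "Randomized, split-mouth, double blinded design clinical trial", so the comparison is paired within patient.

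Section 17.1 narrows the trial to one primary endpoint, recession depth, and says: "The change in recession depth during the study observation period will therefore be used for the calculation of sample size". The inputs are "Standard deviation in the group A: 0.91", "Standard deviation in the group B: 0.95", "Correlation: 0.46", significance level 0.05, power 80%, "Type of test: 2-sided", and "Effect size (the difference in the reduction in recession depth between the test and control groups): 0.4 mm". The result is 48 subjects, raised to 52 for four dropouts. The parameter estimates come from 28 cases already treated in this trial. Section 17.2 refers back to 17.1 for the power analysis.

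No section gives a non-inferiority margin, a direction for the 0.4 mm or a confidence-limit criterion. The only test named elsewhere is a pre/post paired t-test for safety data (section 19.8).

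**The concern.** Non-inferiority has no meaning without a margin: the claim is that PST is not worse than CTG by more than a stated amount. The margin is also an input to the sample size, and section 17.1 has already fixed the sample size without one. The 0.4 mm is labelled as a difference to detect.

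The two sections therefore describe different trials. The 80% in 17.1 is the chance of finding a difference if one of 0.4 mm exists. It says nothing about the chance of showing non-inferiority if PST is as good as CTG.

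The hypothesis matters to the trial's rationale. Section 3.1 presents CTG as the accepted standard and PST as a way of avoiding a second surgical site, so a finding that PST is not inferior would be the headline result. With no rule in the protocol, a non-significant difference could be offered as that finding, although it would not support it.

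**Working it through.** **Inputs**, all from Protocol 17.1: SDs 0.91 and 0.95, correlation 0.46, difference 0.4 mm, 2-sided alpha 0.05, power 80%, n = 48.

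**1. SD of the within-patient difference.**

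√(0.91² + 0.95² − 2 × 0.46 × 0.91 × 0.95) = √(0.8281 + 0.9025 − 0.7953) = √0.9353 = 0.967 mm.

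**2. Reproducing the plan's 48.** The normal approximation is ((1.960 + 0.842) × 0.967 / 0.4)² = 45.9, so 46. The paired t-test (noncentral t) gives 80.1% power at n = 48 and 79.3% at n = 47, so 48 is the exact answer. Other readings do not match: a one-sided 5% paired test needs 38, and an unpaired comparison needs 85 per group. The stated figure is that of a 2-sided paired test for a difference.

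**3. What a non-significant result would mean.** At n = 48 the standard error is 0.967 / √48 = 0.140 mm, and the 95% CI half-width is 0.281 mm. The result is non-significant whenever the observed difference lies within ±0.281 mm. Under a 0.4 mm margin (an assumption, since none is stated), non-inferiority would require the observed PST deficit to be below 0.4 − 0.281 = 0.119 mm. An observed deficit between 0.119 and 0.281 mm is therefore non-significant without excluding a 0.4 mm deficit.

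**4. Error if p>0.05 were read as not inferior.** With PST truly 0.4 mm worse, the chance of p>0.05 is 1 − 0.801 = 0.199, about 20%. The confidence-limit rule with a 0.4 mm margin passes PST 2.5% of the time at that same deficit, because this is the boundary of a one-sided 0.025 test.

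**5. Power for non-inferiority.** One-sided 0.025, paired, SD 0.967, noncentral t with noncentrality (margin − true deficit) × √n / 0.967. The margins are assumed, to show the range.

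| Margin (mm) | True PST deficit (mm) | Power at 48 pairs | Pairs for 80% |
|---|---|---|---|
| 0.4 | 0 | 80% | 48 |
| 0.3 | 0 | 56% | 84 |
| 0.2 | 0 | 29% | 186 |
| 0.4 | 0.1 | 56% | 84 |

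The first row equals the plan's figure because the two calculations share the same arithmetic, with 0.4 mm as the margin in one and as the difference to detect in the other. The protocol uses it only as the latter.

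**The case against.** Much can be said for the plan. The 2-sided setting is an input to the sample size, and 17.1 names no efficacy test. The 95% CI that matches a 2-sided 5% test is the very tool a non-inferiority rule uses. Section 1.1 speaks of comparing efficacy, and 17.1 repeats that aim, so 1.2 may be loosely worded. A statistical analysis plan may exist and contain a rule. These points limit the finding but do not remove it: the contradiction lies between two statements in the protocol, and a margin that should have driven the sample size cannot be left wholly to a later document.

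A reader might infer more than the documents support:

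- *That the trial cannot answer its question.* The data could answer it once a margin is set. What is missing is the criterion.
- *That the plan treats p>0.05 as proof of non-inferiority.* It does not say so. The 20% is conditional on that reading. A significant result in favour of PST would also show that it is not inferior.
- *That the plan assumes a true 0.4 mm difference, which would contradict non-inferiority.* The 0.4 mm is a difference to detect, with no direction stated, and not a belief about the truth.
- *That non-significant results at true deficits of 0.2 or 0.3 mm are also false claims.* Under a 0.4 mm margin such deficits are non-inferior. They are errors only under a smaller margin.
- *That the sample size is certainly adequate, or certainly too small.* Either depends on a margin that the protocol does not give.

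**Conclusion.** The point holds and needs correction. The hypothesis in 1.2 and the sample size in 17.1 disagree, and the 80% power belongs to a difference test. The plan's arithmetic is right for the test it describes.

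The size of the problem depends on the margin. At 48 pairs, power for non-inferiority is 80% only if 0.4 mm is accepted as the margin and the techniques are truly equal. It falls to 56% with a 0.3 mm margin or with a true deficit of 0.1 mm against a 0.4 mm margin, and to 29% with a 0.2 mm margin. These figures rest on the SDs and correlation in 17.1, on 48 evaluable pairs and on a one-sided level of 0.025.

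**What to change.** Either of two repairs restores consistency.

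**Keep non-inferiority.** In 17.1:
- State a margin for the mean within-subject difference (CTG minus PST) in recession-depth reduction at one named time point. Visits run from 6 weeks to 24 months, and 17.1 refers only to the observation period.
- Justify the margin on clinical grounds, independently of the 28 treated cases that supplied the parameter estimates.
- Declare non-inferiority only if the upper limit of the two-sided 95% CI is below the margin, and say that a non-significant difference test is not evidence of non-inferiority.
- Restate the power for the chosen margin and an explicit assumed true difference.

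In 1.2, limit the hypothesis to recession depth. It now covers outcomes in general, and section 2.1 also lists pain and healing as primary.

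**Or drop non-inferiority.** Reword 1.2 as a 2-sided comparison of recession-depth reduction, which the present sample size supports, and make no non-inferiority claim from p>0.05.

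The second repair costs only wording. The first costs wording and a margin justification, and 48 pairs (52 enrolled) stand if 0.4 mm can be justified and zero true difference is a reasonable assumption. With no true difference, a 0.3 mm margin would need 84 evaluable pairs and a 0.2 mm margin 186, before dropout, unless the lower power is accepted and stated.

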2.0 Scientific Endpoints

2.1 Describe the scientific endpoint(s), the main result or occurrence under study.

*NOTE: Scientific endpoints are outcomes defined before the study begins to determine whether the objectives of the study have been met and to draw conclusions from the data. Include primary and secondary endpoints. Some example endpoints are: reduction of symptoms, improvement in quality of life, or survival. Your response should **not** be a date.*

Response:

Primary endpoints: 1) Complete root coverage determined by recession classification, percentage root coverage, and recession depth, 2) Pain Index, 3) Healing Index.

Secondary Endpoints: Improved periodontal parameters; clinical attachment level, probing depth, width of keratinized tissue, gingival thickness, and gingival index.

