
The following measurements will be recorded at baseline, 6 weeks, 3, 6, 12, 18, and 24 months post-surgically:

- I. Complete root coverage (CRC): The number of sites that resulted in 100% root coverage.
- II. Recession Depth (RD): Measured in millimeters from the gingival margin at the mid-buccal aspect of the root, to the CEJ or relative CEJ.

- III. Percentage root coverage (%RC): calculated as $([RD \text{ preoperative} - RD \text{ postoperative}] / RD \text{ preoperative}) \times 100\%$.
- IV. Recession classification: The recession type will be classified according to the criteria suggested by Miller
- V. Probing depth (PD): Measured in millimeters from the gingival margin to the base of the periodontal sulcus at 6 sites per tooth.
- VI. Clinical attachment level (CAL): Measured in millimeters from CEJ or relative CEJ to the base of the periodontal sulcus at 6 sites per tooth.
- VII. Width of the keratinized tissue (KTW): Measured in millimeters at mid-buccal aspect of the tooth from the gingival margin to the mucogingival junction.
- VIII. Gingival Thickness: Measured in millimeters at the mid-buccal of the gingiva and 2 mm apical the gingival margin at the attached gingiva or the alveolar mucosa using a #15 endodontic reamer with a silicon disk stop.
- IX. Plaque index (PI): Is used for estimating the status of oral hygiene by measuring dental plaque that occurs in the areas adjacent to the gingival margin.
- X. Gingival index (GI): GI is measured according to Loe and Sillness and scored on a scale of 0 to 3.

More measurements include:

- ❖ Healing index (HI): A horizontal scale from 1-5 evaluating tissue color, response to palpation, granulation tissue, incision margin, suppuration, adopted from Aleksic²⁵. To be assessed at day 1 and 2 weeks post-surgically as follows:
 - 1 (very poor)= $\geq 50\%$ of the gingiva is red, bleeding on palpation, presence of granulation tissues, incision margin not epithelialized (loss of epithelium beyond incision margin), and presence of suppuration.
 - 2 (poor)= $\geq 50\%$ of the gingiva is red, bleeding on palpation, presence of granulation tissues, incision line not epithelialized (connective tissue exposed), and no suppuration.
 - 3 (good)= 25-50% of the gingiva is red, no bleeding on palpation, no granulation tissues, no connective tissue exposed, and no suppuration.

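### Sections 2.1 and 17.1 of the protocol contradict each other on the primary endpoint; the stated alpha, power and N fit only recession depth as sole primary

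*Protocol*

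**What the plan says.** Section 2.1 sets out the primary list in three numbered items: "Primary endpoints: 1) Complete root coverage determined by recession classification, percentage root coverage, and recession depth, 2) Pain Index, 3) Healing Index". Recession depth appears there only as one of the measures behind item 1. Pain and healing are not in the secondary list of 2.1.

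Section 17.1 takes a different position: "We therefore will focus in this clinical trial on one primary endpoint, namely recession depth". It goes on: "The change in recession depth during the study observation period will therefore be used for the calculation of sample size". The design inputs end with "Level of significance: 0.05" and "Type of test: 2-sided", at 80% power, giving 48 subjects, or 52 with 4 dropouts. No visit is named. Section 10.1 schedules six post-operative measurement visits, at 6 weeks and at 3, 6, 12, 18 and 24 months.

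Two other places bear on the point. Section 1.2 states the hypothesis in the plural: "Pinhole Surgical Technique outcomes are not inferior to those of the Connective Tissue Graft surgical technique". Section 10.1 gives the working definition of the coverage endpoint: "Complete root coverage (CRC): The number of sites that resulted in 100% root coverage".

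**The concern.** A reader of 2.1 and a reader of 17.1 would judge the same result differently. Section 3.1 argues for the pinhole technique partly because it avoids a second surgical site and the pain that goes with it. A plausible outcome is therefore less pain with an inconclusive result on recession depth. Under 2.1 that is a success on a primary endpoint. Under 17.1 the trial has missed its only primary endpoint.

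The error rate and power are also at stake. Only recession depth has been sized. If the list in 2.1 governs, either the 5% or the 80% needs restating, depending on how the three items combine. Section 17.1 reports that 28 cases have already been treated, so data on all the candidate endpoints are accruing while both lists stand.

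**Working it through.** **1. Reproduce the plan's own figure.** Inputs from 17.1: SDs 0.91 and 0.95 mm, correlation 0.46, difference 0.4 mm, two-sided 0.05, power 80%. The comparison is within subject (split-mouth).

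- SD of the difference = √(0.91² + 0.95² − 2 × 0.46 × 0.91 × 0.95) = √(0.8281 + 0.9025 − 0.7953) = √0.9353 = 0.967 mm.
- Normal approximation: n = [0.967 × (1.960 + 0.842) / 0.4]² = 45.9, so 46.
- Exact paired t-test (noncentral t): power is 79.3% at n = 47 and 80.1% at n = 48, so n = 48, as stated.
- 48 + 4 = 52, as stated.

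The calculation uses one endpoint at the full 0.05. No alpha is set aside for any other endpoint.

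**2. Recession depth as sole primary (17.1).** Type I error 5%, power 80.1%, N = 48. All three stated figures hold.

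**3. Any one of the three items in 2.1 suffices, each at unadjusted two-sided 0.05.**

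- Independent tests: 1 − 0.95³ = 1 − 0.857 = 14.3%. This counts a false difference in either direction.
- With three equally correlated normal test statistics (simulation, 400,000 draws; the correlations are assumptions, since the protocol gives none):

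| Assumed correlation | Familywise error |
|---|---|
| 0 | 14.3% |
| 0.3 | 13.7% |
| 0.5 | 12.6% |
| 0.8 | 9.9% |

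- Restoring 5% by Bonferroni gives 0.05 / 3 = 0.0167 per test. Taking item 1 to be judged on recession depth, power at n = 48 falls to 65%, and 80% power needs n = 65.

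**4. All three items must succeed.** Type I error stays at or below 5%. If each test had 80% power and the tests were independent, joint power would be 0.8³ = 51%. Positive correlation would raise this, but never above the 80% of a single test. The 80% for items 2 and 3 is itself an assumption, because the protocol gives no variance or target difference for pain or healing.

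**5. Compare.** Of the three readings, only the one in step 2 makes alpha 0.05, power 80% and N = 48 true together.

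**The case against.** The best defence is that 17.1 is the analysis section. It makes a deliberate choice of a single endpoint, gives a reason, and was revised using data from treated cases. On that view 2.1 is just text that was not brought into line. This is probably how the conflict arose, and it points to the right repair. It does not remove the conflict: 2.1 is current, is the section that defines endpoints, and is not qualified by 17.1.

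A reader might go further and infer that the 5% error rate fails outright. The documents do not support that. Under 17.1 the rate is 5%, and it is also kept if all three items must succeed. It fails only if any one item counts without adjustment. No section states that rule, and the plural hypothesis in 1.2 reads more naturally as all outcomes than as any. A decision rule may also sit in an analysis plan that is not at hand, so the lack of one here is not the fault.

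A reader might also count five separate primary measures in 2.1 and quote 1 − 0.95⁵ = 22.6%. That does not stand. Section 2.1 gives the three measures in item 1 as what coverage is judged from, not as separate tests. By the formula in 10.1, percentage coverage is a function of recession depth, and 100% coverage is the same event as a post-operative depth of zero, so independence is impossible.

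Nor are there two rival definitions of complete root coverage. Section 2.1 names the measures and 10.1 gives the threshold. The part played by recession classification is loosely worded, but no conflicting threshold appears.

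Finally, pain and healing matter to the trial's rationale, and section 22.1 names both. Keeping them primary would be legitimate if the any-or-all rule, alpha and N were stated to match.

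**Conclusion.** The contradiction is real and should be corrected. It is an inconsistency between two current sections, not proof of an inflated error rate. The design figures are right for recession depth alone: N = 48 reproduces exactly.

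Under the other two readings, the cost is a familywise error of up to 14.3% (independence; about 10 to 14% at assumed correlations of 0.8 to 0.3), or joint power of about 51% (independence and 80% power for each assumed). Since the protocol adopts neither rule, these figures show what the ambiguity could cost.

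The unnamed visit adds to it: even under 17.1, six scheduled visits could supply the primary result.

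**What to change.** Amend 2.1 to match 17.1:

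- **Primary:** the reduction in recession depth from baseline to one named visit, worded identically in 2.1 and 17.1. Choose the visit with section 11.2 in mind, which gives participation as 12 to 24 months.
- **Secondary:** complete root coverage (100% coverage, as in 10.1), percentage coverage, Pain Index and Healing Index, reported with confidence intervals, alongside the periodontal parameters already listed.

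If the sponsor prefers to keep several primaries, state whether any or all must succeed and give alpha and N to match.

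The first route changes wording only and leaves N at 48 (52 with dropouts). The sponsor should confirm that the SDs and correlation in 17.1 refer to the visit chosen, which the protocol does not say. The cost is that pain and healing lose primary status, so a benefit there would support the conclusion but could not carry it. The amendment does not settle how the non-inferiority hypothesis in 1.2 relates to the two-sided test in 17.1, which is a separate matter.

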3.0 Background

3.1 Provide the scientific or scholarly background, rationale, and significance of the research based on the existing literature and how it will contribute to existing knowledge. Describe any gaps in current knowledge. Include relevant preliminary findings or prior research by the investigator.

Response:

Gingival recession is defined as the apical migration of the marginal gingiva and it leads to root surface exposure. It may be localized to a few sites or generalized to several teeth, and the severity may vary within the same person and between different people. A commonly used classification of gingival recession is based on the apical relation of the recession to the mucogingival junction and the level of interproximal bone and gingiva ¹.

Data from the third National Health and Nutrition Examination Survey (NHANES III) conducted between 1988 and 1994 show that approximately 24 million U.S. adults had one or more tooth surfaces with ≥ 3 mm of gingival recession ². With an aging population, the number of recession cases in the U.S. is certain to soar. Several etiological factors may cause gingival recessions, including traumatic tooth brushing, malposition teeth, periodontal disease, frenum and bridle insertions, subgingival restorations, maladapted crowns, extraction of adjacent teeth, orthodontic movement, iatrogenic factors, and bone dehiscence ³.

A variety of surgical techniques have been recommended to attain root coverage, including connective tissue graft ^{4,5}, free gingival graft (FGG) ^{6,7}, pedicle flaps ^{8,9}, double papilla grafts ^{10,11}, coronally positioned flaps ¹²⁻¹⁵, coronal positioning of previously placed FGG ¹⁶, guided tissue regeneration (GTR) ¹⁷, and the use of acellular dermal matrix (ADM) ¹⁸, or enamel matrix derivatives ¹⁹. A recently developed technique used to attain root coverage is the Pinhole Surgical Technique (PST) described by [name] ²⁰. This novel approach involves the separation of the gingiva and periosteum from the underlying bone with instruments inserted through a pinhole created in the vestibular area of the involved tooth while filling underneath the undermined interproximal papilla with strips of a bioresorbable membrane, rather than transferring gingival tissue from the palate to the area of recession ²⁰. The advantage of this technique is the preservation of the gingival tissues and its blood supply, while freeing the flap from its apical attachment for ease of coronal displacement and adequate root coverage. In addition, the lack of a secondary surgical site may eliminate the accompanying pain and discomfort often reported in root coverage procedures.

The connective tissue graft technique was described by Langer and Langer in 1985, in which the patient's own connective tissue is taken mostly from the palate and used to cover the area of recession⁵. The retro-molar pad area (tuberosity) has also been used because of the thickening of the sub-mucosa in that area. This graft material is carefully sutured into place and a coronally advanced flap placed and sutured over it, while part of the graft can be left exposed. Currently the connective tissue graft (CTG) is the most common and predictable treatment for gingival recession, and is considered the gold standard²¹. Key advantages of the connective tissue graft procedure are the availability of two sources of blood supply to the graft: one from the recipient bed, and the other from the overlying flap, the perfect chromatic integration, an optimal esthetic outcome, and excellent color match. In addition, an increase in the thickness of the gingival tissues and the width of keratinized gingiva has been documented with the ability for creeping attachment which is not possible with the use of bioresorbable collagen membranes^{18, 22}.

3.2 *Include complete citations or references.*

Response:

